#### **4.3.7. Presentations by Study Visit**

Results from efficacy assessments and safety will be summarized by study visit and treatment group. All assessments will be assigned to an analysis visit window using the study day ranges described in Table 1. All study days up to and including Day 1 are considered the baseline eligible analysis visit window. The last non-missing assessment in the baseline analysis visit window will be used for the baseline summary presentations. If assessments are collected multiple times within a given analysis visit window, the result closest to the target study day, regardless of whether scheduled or unscheduled, will be used for summary presentations. If two measurements have the same distance to the target study day, the first assessment will be used in the summary presentations. All assessments will be presented in the listings.

**Table 1: Visit Windows**

Nominal Visit	Target Study Day	Analysis Visit	Study Day Range
Screening	-30 to -1	Baseline	≤1
Day 1	1		
Week 2	15	Week 2	[12 – 22]
Week 4	29	Week 4	[23 – 42]
Week 8	57	Week 8	[43 – 70]
Week 12	85	Week 12	[71 – 98]
Week 16	113	Week 16	[99 – 126]
Week 20	141	Week 20	[127 – 154]
Week 24	169	Week 24	[155 – 182]

For the post-treatment visit 10, the analyses will be based on the nominal study visit as reported on the CRF.

#### **4.4. TIMING OF ANALYSES**

When all subjects have completed study AA-501-AUAT-201 or terminated early from the blinded treatment period and the database has been locked and forwarded for analysis, the study will be unblinded and the safety and efficacy analysis will be performed according to this SAP.

No interim analysis is planned for this study

#### **5. ANALYSIS POPULATIONS**

The populations for analysis will include the intent-to-treat population (ITT), the safety population (SAF), the per protocol (PP) population, and the pharmacokinetics (PK) population.

##### **5.1. INTENT-TO-TREAT (ITT) POPULATION**

The ITT population is the population of all subjects who are randomized into a treatment group. Subjects in this population will be analyzed according to the treatment group to which they were randomized. The ITT population will be used for all efficacy analyses.

##### **5.2. SAFETY POPULATION**

The Safety population is defined as all randomized subjects who received at least one dose of study medication. Subjects in this population will be analyzed according to the treatment which they receive. All safety analyses will be based on this population.

### **5.3. PER PROTOCOL (PP) POPULATION**

The Per-Protocol (PP) population is defined as all subjects who are randomized and do not have any major protocol violations. Major protocol violations that will lead to exclusion from the PP are defined as:

1. Inclusion or Exclusion criteria not met
2. Concomitant medications taken during the study that interfere with efficacy
3. Did not administer at least 75% of study medication
4. Did not complete Week 24 (Visit 9).

This population will be used for supportive analyses of key efficacy endpoints.

### **5.4. PHARMACOKINETICS (PK) POPULATION**

The Pharmacokinetics (PK) population is defined as all subjects who receive at least one dose of study medication and have at least one measurable ATI-502 concentration value. Subjects in this population will be analyzed according to the treatment which they receive. All PK analyses will be based on this population.

## **6. STATISTICAL METHODS**

Descriptive statistical methods will also be used to summarize the data from this study, with hypothesis testing performed for the primary and key secondary efficacy endpoints. Unless stated otherwise, the term “descriptive statistics” refers to number of subjects, mean, median, standard deviation, minimum, and maximum for continuous data, and frequencies and percentages for categorical data. For categorical variables, the denominator of percentages will be the number of subjects in the treatment group, except for those collected by study visit and/or scheduled time point, in which case the denominator of percentages will be the number of subjects with a non-missing value at the visit and/or the scheduled time point. If a different denominator is used, this will be identified in the summary table.

All data collected during the study will be included in data listings. Unless otherwise noted, the data will be sorted first by treatment group, subject number, and then by date within each subject number.

The term ‘treatment group’ refers to ATI-501 active groups and matching Placebo Oral Suspension group.

All statistical testing will be two-sided and will be performed using a significance (alpha) level of 0.05 unless otherwise stated. P-values will be presented to three decimal places. For the efficacy

endpoints, the ATI-501 treatment groups will be tested versus Placebo Oral Suspension via statistical inference.

The statistical analyses will be conducted with the SAS® software package version 9.4 or higher. All analyses will be subject to formal verification procedures. Specifically, results will be independently verified by a second programmer/statistician prior to issuance of the draft statistical report. All documents will be reviewed by the lead statistician to ensure accuracy and consistency.

#### **6.1. SUBJECT DISPOSITION, DEMOGRAPHIC AND BASELINE CHARACTERISTICS**

Subject disposition will be presented for all subjects in the ITT population. The number of subjects who completed the study or early terminated from the study during the blinded treatment period will be provided. The reasons for early termination will be presented by treatment group. Additionally, the number of weeks on study will be summarized for all treated subjects.

Demographic data, including age, gender, race, ethnicity, and Fitzpatrick skin type, and screening weight (kg) and height(cm) will be summarized using descriptive statistics by treatment group. This information will be reviewed for baseline differences, but no statistical testing will be performed.

Baseline characteristics, including diagnosis type (Areata, Universalis, Totalis), ophiasis pattern of hair loss, duration of alopecia, duration of current episode of alopecia (continuous and dichotomized (< 4 years, ≥ 4 years)), baseline hair pull test results (dislodged hairs and broken hairs), baseline vellus and indeterminate hair assessment, baseline SALT score group (<50%, >50%) and baseline Scalp-ClinRO (target patch and entire scalp) and Scalp-PRO (target patch and entire scalp) will be reported.

Alopecia treatment history will be summarized. The count and percent of subjects using the therapies pre-specified on the History of Alopecia CRF page will be reported.

Medical history will be summarized using the pre-specified CRF body system categories. The count and percent of subjects reporting a condition in the body system will be reported.

Findings from the baseline physical examination (PE) will also be summarized using the pre-specified body system categories and include reporting of abnormal not clinically significant (NCS) and abnormal clinically significant (CS).

Prior and concomitant medications will be coded using the World Health Organization (WHO) Drug Dictionary (version WHO-DD – March 2019) for the entire period of the study. Prior and concomitant medications will be summarized in tables and may be presented in data listings.

Study drug exposure and compliance will be summarized by treatment. The study drug duration along with summaries of missed doses, dose reductions, and treatment compliance will be reported.

## **6.2. EFFICACY ANALYSIS**

### **6.2.1. Primary Efficacy Endpoint**

The primary efficacy variable will be the mean percent change from baseline in the SALT score at Week 24 (Visit 9).

### **6.2.2. Primary Efficacy Analysis**

Descriptive statistics for the SALT score, change, and percent change from baseline will be presented by analysis visit. Percent change from baseline in SALT over time up to Week 24 will be analyzed using a mixed effect for repeated measures (MMRM) model. This primary analysis will utilize the score with imputation for LOCF and will be based on the ITT population. The model will include fixed effect terms for treatment, study visit, and treatment by study visit interaction. Within-subject variability will be modeled using a compound symmetry covariance structure. The least squares mean (LS Mean) percent change from baseline in the SALT score at each visit, estimated from the MMRM model, with the estimated standard error and 95% confidence interval (CI), will be presented in tabular and graphic format. The difference in the adjusted means between treatment groups and the associated 95% CI of the difference will be provided.

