**Statistical Methods**

The primary efficacy variable will be the percent change from Baseline in the SALT score at Week 24 (Visit 9). This represents the percentage of hair regrowth. It will be calculated as the change from baseline (Visit 2) to Week 24 (Visit 9), divided by the baseline and expressed as a percentage.

Missing data for the primary endpoint will be imputed using Last Observation Carried Forward (LOCF) methodology. The analysis will be conducted on the percent change from baseline over time including all visits using a mixed effect model repeated measures (MMRM). The adjusted mean (LS Mean) for percent change from baseline in the SALT score at each visit, estimated from the MMRM, with the estimated standard error and 95% confidence interval (CI), will be presented in tabular and graphic format. The difference in the adjusted means between treatment groups and the associated 95% CI of the difference will be provided. No adjustment for multiplicity will be made. The model

will include fixed effect terms for treatment, study visit, baseline SALT score group (<50, >=50), and treatment by baseline SALT group interaction. The primary analysis will be based on the Intent-to-Treat (ITT) population. Statistical significance for primary efficacy endpoint will be declared if at least one treatment group comparison at the Week 24 visit has a two-sided p-value less than or equal to 0.05.

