### 9.4.1. Primary Efficacy Analyses

The primary efficacy variable will be the percent change from Baseline (Visit 2) in the SALT score at Visit 9 (Week 24). Missing data for the primary endpoint will be imputed using Last Observation Carried Forward (LOCF) methodology. The analysis will be conducted on the percent change from baseline over time including all visits using a mixed effect model repeated measures (MMRM). The adjusted mean (LS Mean) for percent change from baseline in the SALT score at each visit, estimated from the MMRM, with the estimated standard error and 95% confidence interval (CI), will be presented in tabular and graphic format. The difference in the adjusted means between treatment groups and the associated 95% CI of the difference will be provided. No adjustment for multiplicity will be made. The model will include fixed effect terms for treatment, study visit, baseline SALT score group (<50, ≥50), and treatment by SALT group interaction. The primary analysis will be based on the Intent-to-Treat (ITT) population. Statistical significance for primary efficacy endpoint will be declared if at least one treatment group comparison at the Week 24 visit has a two-sided p-value less than or equal to 0.05.

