### 9.4.2. Secondary Efficacy Analyses

A secondary sensitivity analysis of the primary endpoint will be conducted using the PP population. This analysis will use the same methodology as described for the primary analysis just applied to the PP population.

The secondary efficacy endpoints include the change from Baseline in the ALODEX score, ASAA (CR & SR), AFHA (CR & SR), PhGIS, SGIS, SGSHQ, AIA, and DLQI as well as the proportion of subjects achieving a ≥ 50% hair growth compared with Baseline based upon the SALT score and ALODEX score, separately. SGITS responses at Week 12, 24, and 28 will be summarized. Various secondary responder efficacy endpoints will be defined based upon the SALT score, the ALODEX score and the AAA (Clinician and Subject) questionnaires. Details of these responder definitions will be specified in the statistical analysis plan (SAP). Global Impression of Change (Clinician and Subject) at Week 24 (Visit 9) will be used in the psychometric evaluation of the scores from the ASAA (CR and SR), respectively. Non-Scalp Hair Loss Assessment, Vellus and Indeterminate Hair Assessment and Hair Quality Assessment including normalization of exclamation point hairs and hair shedding will be described. The analysis for the percent change in ALODEX score will use the same methodology as specified for the primary efficacy analysis. Other parameters will be analyzed as detailed in the SAP.

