### **4.3. HANDLING OF DATA**

#### **4.3.1. Strata and Covariates**

No stratified analyses are planned.

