## **7. CHANGES IN THE PROTOCOL-SPECIFIED ANALYSES**

All analyses specified in the SAP are consistent with those specified in the protocol. Should any deviations from the analyses specified in the authorized statistical analysis plan arise, such deviations will be documented in the final clinical study report.

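### The protocol and the SAP specify different primary models: the protocol's cannot isolate Week 24, the SAP's drops baseline SALT, and SAP section 7 says nothing changed

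*SAP*

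**What the plan says.** Protocol 9.4.1 builds the primary MMRM from "fixed effect terms for treatment, study visit, baseline SALT score group" (below 50 against 50 or more) and treatment by SALT group. The synopsis closes the same list with "and treatment by baseline SALT group interaction". Both promise adjusted means visit by visit. Both declare success if "at least one treatment group comparison at the Week 24 visit has a two-sided p-value" of 0.05 or less. Neither lists treatment by visit.

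SAP 6.2.2 says: "The model will include fixed effect terms for treatment, study visit, and treatment by study visit interaction". It adds compound symmetry and has no baseline term. Under the heading Strata and Covariates, SAP 4.3.1 says only "No stratified analyses are planned". SAP 4.3.2 and 6.2.7 keep SALT group for subset analyses.

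SAP 4.4 indicates which model will be run: "the safety and efficacy analysis will be performed according to this SAP". SAP section 7 asserts: "All analyses specified in the SAP are consistent with those specified in the protocol".

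**The concern.** The two lists share only treatment and visit, and no text reconciles them. A reader cannot tell whether the change was intended. Section 7 undertakes to report deviations from the SAP, not departures of the SAP from the protocol, so nothing commits the sponsor to disclose it.

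Each model also has its own weakness. The protocol's gives one difference for all visits, so anyone fitting it as written would report a visit-combined difference as the Week 24 effect. The SAP's targets Week 24 but gives up precision from a score already collected, with 95/4, or about 24, subjects per arm. Two candidate models also leave room to choose between them after unblinding.

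The conflict reaches a secondary endpoint. Protocol 9.4.2 says "The analysis for the percent change in ALODEX score will use the same methodology as specified for the primary efficacy analysis", and SAP 6.2.5 likewise points back to its own primary model.

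**Working it through.** **The plan's own power figure.** SAP 4.1 gives at least 84% power for the primary analysis. With 95 × 0.9 / 2 ≈ 43 per pooled group, 32% against 6% and two-sided 0.05, power is 84.4% (Fisher exact), 84.9% (continuity-corrected) or 88.1% (pooled z). The figure reproduces, but it describes a pooled responder comparison and depends on neither MMRM.

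**The two models side by side.**

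| | Protocol 9.4.1 and synopsis | SAP 6.2.2 |
|---|---|---|
| Treatment, visit | yes | yes |
| Treatment by visit | no | yes |
| Baseline SALT group | yes | no |
| Treatment by SALT group | yes | no |
| Covariance | not named | compound symmetry |
| Visits | every visit | stops at Week 24 |
| Week 24 success rule | stated | not repeated |

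**What the protocol model estimates.** With its terms, the dose-minus-placebo difference in SALT group *g* is τ + τ_g. No visit index appears, so the difference is the same at Week 4 and Week 24. With complete data and compound symmetry, the estimate is the equal-weight average over visits. A check fitted treatment plus visit, with and without their interaction, to 60 simulated complete datasets (Weeks 4 to 24, linear true effect reaching 30 points; assumed SD 40, correlation 0.6):

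- Without the interaction, the treatment coefficient equalled the raw average of the visit differences to rounding error (mean 18.52; expected 17.5).
- With it, the Week 24 contrast equalled the raw Week 24 difference (mean 31.09; expected 30).

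Another covariance changes the visit weights but does not isolate Week 24. AR(1) with correlation 0.85 puts 0.385 on each of the first and last visits and 0.058 on each of the other four.

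**Share of the Week 24 effect returned** = mean over visits of effect(week)/effect(24). The documents give no time course, so these are assumed. SALT is scheduled at Weeks 2, 4, 8, 12, 16, 20, 24 and 28.

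| Time course | Weeks 2–24 | Weeks 4–24 |
|---|---|---|
| Linear | 86/168 = 51% | 84/144 = 58% |
| Onset after Week 4 | 43% | 50% |
| Onset after Week 8 | 36% | 42% |
| Plateau from Week 12 | 74% | 83% |

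Adding Week 28, with the Week 24 effect held, gives 110/192 = 57% for linear growth over Weeks 2 to 28.

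**Test statistic.** Averaging also lowers the standard error, by the factor √((1 + (K−1)ρ)/K) under compound symmetry. The z ratio is the share divided by this factor. For a contrast with 80% power at Week 24, power becomes Φ(ratio × 2.80 − 1.96).

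| Linear growth | ρ = 0.4 | ρ = 0.6 | ρ = 0.8 |
|---|---|---|---|
| Weeks 2–24 (K = 7): SE factor | 0.697 | 0.811 | 0.910 |
| z ratio | 0.735 | 0.631 | 0.562 |
| Power | 54% | 42% | 35% |
| Weeks 4–24 (K = 6): z ratio | 0.825 | 0.714 | 0.639 |
| Power | 64% | 52% | 43% |

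With a plateau from Week 12 (Weeks 2 to 24), the z ratios are 1.059, 0.911 and 0.811. A simulation with 24 per arm, SD 40, ρ = 0.6 and a true linear effect of −30 at Week 24 gave −15.3 (SE 9.4) for the visit average and −30.0 (SE 11.6) for the Week 24 contrast.

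**Cost of omitting baseline in the SAP model.** The SE relative to a baseline-adjusted model is 1/√(1 − R²): 1.054 at R² = 0.1 and 1.195 at R² = 0.3. Both R² values are assumed.

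**The case against.** The strongest reply is that the SAP model will be run, it targets Week 24, and omitting baseline does not bias a randomised comparison. The effect shares and power figures then describe an analysis nobody intends. That is fair as to the likely harm. It does not excuse section 7, which denies a change that was made.

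A second reply is that by promising means at each visit and a test at Week 24, the protocol implies the interaction. That is a plausible reading, but the term is unwritten in both places where the model is given, and the baseline terms conflict either way.

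Third, the sizes are soft. They combine the protocol's fixed effects with the SAP's covariance. Including Week 2 is arguable, because the schedule's first footnote says Visit 3 efficacy assessments test the reliability of the outcome tools. Using Weeks 4 to 24 raises power to 64%, 52% and 43%. The size moves, but the conclusion does not.

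Fourth, the 5% to 20% loss is measured against a baseline-adjusted model, not against the protocol's. This stands. If the protocol's treatment effect weights the two SALT groups equally (the weighting is unstated), its SE is multiplied by 1/√(4p(1−p)) before any gain from variance explained. That is 1.25 if 20% of subjects are below 50 and 1.67 if 10% are (assumed shares). Dropping both terms could therefore be more precise than the protocol model. The better comparison is with a model that keeps baseline as a main effect.

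**Conclusion.** The concern holds. The primary fixed effects differ, no text reconciles them, and the consistency statement in SAP section 7 is wrong for the primary analysis. That much rests on the wording alone.

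Read literally, the protocol model cannot produce its own Week 24 test. Under the assumed time courses it would return 36% to 83% of the Week 24 effect over visits to Week 24. The loss of power ranges from none (early plateau, low correlation) to substantial (80% down to 35% with linear growth over Weeks 2 to 24 and correlation 0.8). These sizes assume complete data and compound symmetry.

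The SAP model asks the right question. Omitting baseline does not bias it, but it forgoes an adjustment that could be worth 5% to 20% in standard error if baseline explains 10% to 30% of the variance. The conflict should be resolved before unblinding.

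**What to change.** State one primary model in both documents: treatment, visit, treatment by visit and baseline SALT, with each dose minus placebo at Week 24 as the primary contrast. Say which visits enter, and repeat the success rule in the SAP. A continuous baseline score with baseline by visit is preferable but a matter of choice. A patchy versus AT/AU factor is optional, since it overlaps with baseline SALT. Leave treatment by SALT group to the subgroup analyses in SAP 6.2.7.

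Replace the consistency sentence in SAP section 7 with the actual changes from protocol 9.4.1: treatment by visit added, and baseline SALT group and treatment by SALT group removed or replaced. Confirm that percent change in ALODEX follows the same model.

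The cost is SAP wording and a short protocol clarification before unblinding. Baseline SALT is already collected, so no new data are needed.

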The ALODEX and SALT assessments are based on terminal hair growth. Another parameter that will be considered will be the normalization of exclamation point hairs. These two features should be trackable irrespective of the subjects’ intrinsic hair color, caliber or density, and should give a meaningful indicator of response to treatment.

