### 4.1. Subject Inclusion Criteria

Subjects must meet the following criteria to be eligible for participation in the study:

1. Able to comprehend and willing to sign an Informed Consent Form (ICF).
2. Male or non-pregnant, non-nursing female  $\geq$  18 years old at the time of informed consent.
3. Have a clinical diagnosis of stable AA, AU or AT (Stable is defined as no current areas of spontaneous terminal scalp hair regrowth).
4. Have a Severity of Alopecia Tool (SALT) score of at least 30% to 100% total scalp hair loss determined by the study investigator at Screening (Visit 1) and Baseline (Visit 2).
5. Subjects with 30% to 95% scalp hair loss (based on SALT score) must have an assessment of “no hair” or “a little hair” in the target scalp patch based on both the Clinician and Subject Alopecia Scalp Appearance Assessment (ASAA). The target patch is defined as the most bothersome patchy area of hair loss as identified by the subject (Refer to Section 7.1).
6. Have a duration of the current episode of stable scalp hair loss for a minimum of 6 months and a maximum duration of hair loss of 12 years (inclusive). [Current episode is defined as the period of the current presentation of hair loss (AA, AU or AT)].
7. If the subject is a woman of childbearing potential (WOCBP), she must have:
  - Negative serum pregnancy tests at Screening (Visit 1); and
  - A negative urine pregnancy test at Baseline (Visit 2); and
  - Agree to not be planning a pregnancy during the study duration and use a highly effective method of contraception during the study and for 30 days after the last dose of study medication. (Refer to Section 8.4.2).
8. Be in good general health and free of any known disease state or physical condition which, in the investigator’s opinion, might impair evaluation of the subject or which might expose the subject to an unacceptable risk by study participation.
9. Be willing to maintain the same hair style and hair dyeing throughout the study period. Subjects who shave their scalp must be willing to refrain from shaving their scalp for at least two weeks prior to each study visit, as determined by the investigator based on the ability to assess visible scalp hair growth. Hair trimming outside the treatment areas to maintain the current hair style is permitted.
10. Be willing and able to follow all study instructions and to attend all study visits.

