#### **Treatment Assignment:**

A total of approximately 95 subjects will be randomized in a 1:1:1:1 ratio:

- Placebo Oral Suspension, twice daily (BID) for 24 weeks (6 months)
- ATI-501 Oral Suspension, 400 mg, BID for 24 weeks (6 months)
- ATI-501 Oral Suspension, 600 mg, BID for 24 weeks (6 months)
- ATI-501 Oral Suspension, 800 mg, BID for 24 weeks (6 months)

During the screening period, subjects will be assessed for eligibility into the study. Subjects will receive ATI-501 Oral Suspension, 400 mg, 600 mg, or 800 mg or Placebo Oral Suspension twice-daily for up to 24 weeks. Assessment of response to treatment will be performed at Week 4 (Visit 4), Week 8 (Visit 5), Week 12 (Visit 6), Week 16 (Visit 7), Week 20 (Visit 8), Week 24 (Visit 9), and post-treatment (Visit 10). Safety and tolerability will be evaluated at each study visit by assessment of adverse events (AEs), clinical lab tests, vital signs, and at select visits, ECGs. The primary analysis will be conducted after all subjects complete Visit 9 or Visit 10.

Subjects who complete Visit 9 (Week 24) will be eligible to enter a 28-week open-label study ATI-502-AA-203. Subjects who decline or are not eligible for ATI-502-AA-203 should be seen for the Visit 10 (Post-treatment) assessments.

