## **4. GENERAL STATISTICAL CONSIDERATIONS**

### **4.1. SAMPLE SIZE AND POWER**

The planned sample size is 95 enrolled subjects with approximately 45 subjects enrolled with AT or AU. It is assumed that the proportion of subjects who achieve at least a 50% reduction in hair loss (SALT50) for the pooled 600mg and 800mg treatment groups will be at least 32%, and the SALT50 for the pooled placebo and 400mg treatment groups will be at most 6%. Assuming a 10% dropout rate, this results in >80% power for the SALT50 analysis. Because the primary efficacy analysis of mean percent change in hair loss using SALT scores is expected to be more sensitive than the SALT50 responder analysis, the power for the primary analysis is also expected to be no less than 84%.

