#### **6.2.5. Secondary Efficacy Analysis**

Descriptive statistics will be presented for all secondary efficacy endpoints.

The mean percent change from baseline in the ALODEX score (percent regrowth); the mean change from baseline in SALT and the mean change from baseline in ALODEX will be analyzed using the methods planned for the primary efficacy analysis. The calculated DLQI total score ranges from 0 to 30. This mean change from baseline in DLQI will also utilize the MMRM analysis as planned for the primary efficacy analysis.

Responder-type analyses are planned based on the SALT, ALODEX, Scalp-ClinRO, and Scalp-PRO. The responder definitions include:

- The proportion of subjects achieving a  $\geq 50\%$  hair regrowth compared with baseline for SALT and for ALODEX scores
- Proportion of subjects achieving an absolute SALT score  $\leq 10$
- Proportion of subjects with  $\geq 2$ -point improvement in Scalp-ClinRO for the Target Area (patchy AA subjects only)
- Proportion of subjects with  $\geq 2$ -point improvement in Scalp-PRO for the Target Area (patchy AA subjects only)
- Proportion of subjects with  $\geq 1$ -point improvement in Scalp-ClinRO for the entire scalp
- Proportion of subjects with  $\geq 1$ -point improvement in Scalp-PRO for the entire scalp

The observed proportion of responders and associated 95% CI will be presented. Adjusted rates and 95% CI will be obtained from a logistic regression model with a factor for treatment. The p-value for the overall global test that  $\beta=0$  for this factor will be presented. The adjusted odds ratios (95% CI) for being a responder (active/placebo oral suspension) will be presented along with the associated p-value.

The questionnaires Scalp-PRO, Scalp-ClinRO, PhGIS, AFHA, and SGIS are collected on a 1-5 scale. The SGRHQ questionnaire is collected on a 1-7 scale. The frequency of responses for each value will be reported by visit and treatment group. Additionally, change status will be categorized as “Better by x points” when the score decreases from baseline by x points, and as “Worse by x points” when the score increases by x points. For these scales, a Wilcoxon rank sum test will be used at each visit to obtain a p-value to compare the change status of each active treatment group to the placebo oral suspension.

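### Compound symmetry in the SAP's primary MMRM bases the Week 24 standard error on the average visit variance, which is too small if spread grows over time

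*SAP*

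**What the plan says.** SAP 6.2.2 analyses percent change from baseline in SALT up to Week 24 in the ITT population after LOCF. The fixed effects are treatment, visit and treatment by visit. On the covariance it says: "Within-subject variability will be modeled using a compound symmetry covariance structure". It names no other structure, fallback, empirical standard error or degrees-of-freedom method. SAP 6.2.3 repeats the same methods in the PP population and on observed data, so those analyses keep the same covariance.

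Protocol 9.4.1 names no covariance structure. It declares success "if at least one treatment group comparison at the Week 24 visit has a two-sided p-value less than or equal to 0.05", with no multiplicity adjustment.

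Under SAP 6.2.5, percent change in ALODEX and absolute change in SALT and ALODEX "will be analyzed using the methods planned for the primary efficacy analysis". DLQI change uses the same MMRM, and SAP 6.2.7 repeats the SALT and ALODEX percent-change models in each subgroup.

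The number of visits in the model is not settled. Protocol 9.4.1 includes all visits and SAP Table 1 defines a Week 2 window. However, SAP 1.1 lists response assessments from Week 4, and footnote 1 of the SAP schedule says the Visit 3 efficacy assessments serve to test instrument reliability.

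**The concern.** Compound symmetry assumes the same variance at every visit. For this endpoint that is the assumption that needs defending:

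- A change from baseline is zero for every subject at baseline.
- Entry requires stable disease ("Stable is defined as no current areas of spontaneous terminal scalp hair regrowth"), and "The ALODEX and SALT assessments are based on terminal hair growth", so early changes should be small.
- The power section expects subjects to divide by Week 24. It takes a 50% regrowth rate of at least 32% in the pooled 600 and 800 mg groups, while the rate "for the pooled placebo and 400mg treatment groups will be at most 6" percent.

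A few subjects moving far while most stay near zero widens the spread over time. If so, the quieter early visits pull down the standard error used at Week 24, which is the decision visit. The nominal 5% tests and 95% intervals would then not hold their level, and intervals that are too narrow would mislead dose selection.

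**Working it through.** **The plan's own figure.** SAP 4.1 gives more than 80% power for 50% regrowth, 32% versus 6%, in pooled groups with N = 95 and 10% dropout, and carries 84% to the primary analysis. With 95 × 0.9 / 2 = 42.75 per pooled group, the normal approximation gives 87.9%. Fisher's exact test gives 84.9% at 42 and 84.4% at 43 per group. The figures reproduce, but they rest on a responder comparison and supply no SD at any visit.

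**Why the average variance is used.** Let e be the residuals from the arm-by-visit means, b each subject's mean residual, T the number of visits and N = 95 in 4 arms. On complete data the compound-symmetry total variance is MSB/T + (T−1)/T × MSE, where MSB = T Σb²/(N−4) and MSE = ΣΣ(e−b)²/((N−4)(T−1)). Adding the terms gives ΣΣe²/(T(N−4)), the plain average of the pooled visit variances. Hence

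SE(Week 24 difference) = √[average visit variance × (1/n1 + 1/n2)].

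A REML fit to one simulated trial of 24/24/24/23 subjects with growing spread gave 4.111. The formula also gave 4.111, whereas the Week 24 variance gave 6.044.

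**Level per comparison.** With r = √(average visit variance / Week 24 variance), the level is 2 × [1 − Φ(1.96 r)]. Example for Weeks 4 to 24 with SD rising linearly from 1.0 to 1.5: the variances are 1, 1.21, 1.44, 1.69, 1.96 and 2.25, with mean 1.592. Then r = √(1.592/2.25) = 0.841 and 1.96 × 0.841 = 1.648, so the level is 9.9%.

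| Assumed SD, first visit to Week 24 | r, 6 visits | Level | r, 7 visits (with Week 2) | Level |
|---|---|---|---|---|
| Falls 1.2-fold | 1.102 | 3.1% | 1.109 | 3.0% |
| Constant | 1.000 | 5.0% | 1.000 | 5.0% |
| Grows 1.2-fold | 0.918 | 7.2% | 0.913 | 7.4% |
| Proportional to time up to Week 12, then flat | 0.871 | 8.8% | 0.809 | 11.3% |
| Grows 1.5-fold | 0.841 | 9.9% | 0.831 | 10.4% |
| Grows 2-fold | 0.769 | 13.2% | 0.754 | 14.0% |
| Proportional to time throughout | 0.649 | 20.3% | 0.602 | 23.8% |

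These assume equal variances across arms. The chance that at least one of three comparisons is significant with no drug effect is about 13% at constant SD, which is the openly unadjusted multiplicity. It is 24% at 1.5-fold and 30% to 32% at 2-fold.

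**Simulation at the plan's response rates.** Inputs were 24/24/24/23 subjects, 10% dropout with LOCF, responders gaining 50% to 100% linearly over 24 weeks, assumed scoring noise SD 5 to 20 points and assumed drift SD 0 to 20 points at Week 24. There were nine noise and drift settings with 6,000 trials each.

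- 6% responders in every arm: the level under compound symmetry is 9% to 20% (6 visits) or 9% to 24% (7 visits). Using the Week 24 variance it is 4% to 6%.
- 6% on placebo and 400 mg, 32% on 600 and 800 mg: 95% intervals for 600 and 800 mg versus placebo cover 79% to 88% (6 visits) or 76% to 87% (7 visits) under compound symmetry, against 94% to 95% with the Week 24 variance.
- In the second case 400 mg versus placebo is little affected: 4% to 10% (6 visits) or 5% to 12% (7 visits). Variance is pooled over arms, and the pooled Week 24 variance makes this comparison conservative (0.2% to 2.3%).

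**The case against.** **The protocol's model does not have the problem.** Protocol 9.4.1 has no treatment-by-visit term; it uses baseline SALT group and its interaction with treatment. Without treatment by visit, the contrast is a difference of subject means over visits, which compound symmetry handles correctly. A simulation (6 visits, 6,000 runs, baseline-group terms omitted) gave 4.9% with SD proportional to time, 5.3% at 2-fold and 5.0% at 1.5-fold. This is correct, and the two models conflict although SAP Section 7 says the analyses agree. It limits the defect to the SAP model but does not repair that model.

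**The growth is assumed.** This stands. A constant SD gives 5% and a falling SD about 3%. The 24% end needs both SD proportional to time and Week 2 in the model. The reliability footnote and SAP 1.1 favour six visits, where the top is about 20%. In the plan's expected scenario the only null comparison with placebo, 400 mg, is at most mildly inflated.

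**This is an exploratory Phase 2 trial with open multiplicity.** SDs by visit will be reported, and the logistic responder analysis does not use this covariance. A distortion could therefore be seen, but the primary p-values and intervals would still be wrong. The accepted multiplicity does not cover the addition from 13% to 24% or more.

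**Conclusion.** The concern holds for the model in SAP 6.2.2. The dependence on the average visit variance is an algebraic fact for that model on LOCF-completed data. The size depends on an unknown growth in spread: with six visits, about 7% for 1.2-fold growth and up to about 20% for SD proportional to time. Growth is the likely direction, and at the plan's own response rates coverage for the two higher doses falls well below 95% across the assumed noise and drift settings. Because this affects the primary p-values and intervals, and nothing else planned corrects it, the SAP should be changed before unblinding.

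**What to change.** In SAP 6.2.2:

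1. Replace compound symmetry with an unstructured covariance and Kenward-Roger degrees of freedom. On LOCF-complete data the Week 24 comparison is then the pooled Week 24 variance test on 95 − 4 = 91 degrees of freedom.
2. Pre-specify an ordered fallback for non-convergence: heterogeneous Toeplitz, heterogeneous AR(1), heterogeneous compound symmetry, each with empirical (sandwich) standard errors. The structures alone are not enough. In 700 trials in each of three settings (6 visits, 6% responders in all arms), compound symmetry gave 10% to 18%, unstructured 4% to 6%, heterogeneous compound symmetry 5% to 7%, and heterogeneous AR(1) and Toeplitz 5% to 11%. Empirical standard errors gave 4% to 6% in 12,000 trials per setting, including the 6%/32% case.
3. Add one sensitivity analysis with empirical or arm-specific variances, since response rates are expected to differ by arm.
4. State whether Week 2 enters the model.

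LOCF stays primary as the protocol specifies, and the planned observed-data analyses take the same covariance; the unstructured fit to observed data was not simulated. No protocol amendment is needed for the covariance. The conflict between the SAP and protocol fixed effects must be reconciled separately.

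The cost is a few lines of SAP text, wider Week 24 intervals if spread grows, a conservative 400 mg comparison if arm variances differ, and possible use of the fallback in small subgroups. Unstructured needs 6 × 7 / 2 = 21 parameters, or 7 × 8 / 2 = 28 with Week 2, which about 95 subjects can support.
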